1.1 Background – Main Study

Tobacco use and obesity are the two leading causes of preventable deaths. Because these two behaviors share common brain reward mechanisms, reducing one behavior often leads to increases in the other behavior. Indeed, ~80% of smokers gain weight after quitting, with an average weight gain >13 lbs. in one year (vs. ~2 lbs. in continuing smokers). Weight gain is often cited as a key reason for delaying quit attempts or relapsing, making post-cessation weight gain (PCWG) a *significant clinical problem*. While a variety of pharmacological and behavioral interventions to reduce PCWG have been tested, these tend not to be effective. To develop better treatments, we need to understand *why* people gain weight after quitting smoking.

Behavioral Economic and Incentive Salience models shed much light on this clinical problem. Smoking cessation produces reward dysregulation that can alter the motivational salience of other reinforcers, particularly food. After stopping smoking, smokers increase their between-meal snacking, especially foods high in fat and sugar. Increases in caloric intake occur within days of quitting smoking, and are clinically significant. In parallel, we have shown that smoking cessation produces working memory deficits and reduces activity in the brain's cognitive control circuits, making it even more difficult to exert self-control over temptations to eat highly rewarding foods. Thus, smokers have a double challenge: food becomes more salient and reinforcing at a time when their neurocognitive resources are compromised.

Neuroimaging can identify mechanisms underlying behavior change beyond self-report and behavioral measures. The proposed functional magnetic resonance imaging (fMRI) study breaks new ground by integrating concepts and tools from the fields of behavioral economics and cognitive neuroscience to accelerate the study of mechanisms underlying PCWG. We will use a previously validated within-subject crossover neuroimaging study design to examine changes in working memory, food salience (cue-induced craving), and food reinforcement processes in the brain after 4 days of smoking cessation (vs. smoking as usual). A non-smoker control group will provide insight into baseline differences from smokers (abstinent and sated). Caloric intake, the primary outcome, will be assessed using 24-hr. food recalls during each study period. We will assess three parallel pathways including: working memory, food cue reactivity, and food reinforcement at the neural and behavioral levels.

1.2 Background – Recruitment & Retention Pilot Study

Nearly one in three clinical trials closely prematurely due to under-enrollment [67]. Reports of clinical trials consistently state that initial approaches to recruitment are rarely successful, take longer and are more costly than planned, and the pool of participants is overestimated [68]. Unfortunately, many studies implement recruitment strategies without taking a systematic approach to identifying the most efficient and cost-effective approaches to enrolling subjects. With the increasing ubiquity of cell phones, text messaging (SMS) interventions have the potential to increase reach and reduce costs. In the United States, it is estimated that 85 to 91% of adults (18 and over) own a mobile phone, and these rates are observed across low- and

CONFIDENTIAL

This material is the property of the University of Pennsylvania. Do not disclose or use except as authorized in writing by the study sponsor

high-income individuals [69]. SMS interventions for improving adherence to antiretroviral treatment in people living with HIV as well as smoking cessation have demonstrated efficacy [70]. However, few studies have explicitly examined strategies to optimize the use of SMS to enhance clinical trial enrollment. Behavioral economic strategies, including information provision and incentives, may represent useful approaches to overcoming barriers to clinical research and ultimately advancing science [71]. Information provision includes utilizing descriptive and injunctive norms, personalization, and reciprocity. Framing messages to shape social norms regarding research participation may increase engagement. For example, in addition to “personal medical benefit”, patients cite “contributing to research that could help other people” and “giving something back in return” as the most important reasons to participate in clinical research [72]. Another common strategy for improving recruitment and retention is to offer incentives, including monetary payments or other rewards that target motivation. For instance, contingency management (CM), where tangible reinforcement is provided in close temporal proximity to a participant performing a target behavior (e.g., on-time attendance) is highly efficacious in engendering target behaviors [73-75]. Although information provision and incentives are effective strategies for behavior change, they may target different aspects of motivation: intrinsic (i.e., the behavior itself is purposive) vs. extrinsic motivation (i.e., the prospect of gaining the incentive motivates the behavior), respectively. Although numerous studies comparing intrinsic vs extrinsic strategies to enhance motivation have yielded inconsistent results, a recent meta-analysis suggested intrinsic and extrinsic factors may act synergistically [76]. Thus, we propose to employ information provision and incentive strategies independently and in combination to evaluate the optimal approach for recruiting and retaining subjects in clinical research studies.

2 Study Objectives

2.1 Main Study

Aim 1: To test three putative brain mechanisms underlying increased caloric intake during nicotine withdrawal using an abstinence challenge paradigm (within-subject).

H1a: Brain signal will be associated with decreased working memory (WM) in the dorsolateral prefrontal cortex (DLPFC) and reduced suppression of activity in the posterior cingulate cortex (PCC).

H1b: There will be increased food cue-induced activity in the insula, anterior cingulate cortex (ACC), orbitofrontal cortex (OFC), and ventral striatum/nucleus accumbens (VS/NAC).

H1c: Increased food reinforcement choice-related activity in VS/NAC and ventromedial prefrontal cortex (vmPFC) will predict increased caloric intake (abstinence vs. smoking).

Aim 2: To evaluate the relative contribution of task-related brain signal (WM, Food Cue Response, Food Reinforcement/Choice) in prediction of nicotine abstinence-induced increase in caloric intake (within-subject).

H2a: Brain responses (H1a-c) will characterize abstinence challenge-induced change in caloric intake more accurately than clinical (age, sex, nicotine dependence, BMI), subjective (craving, withdrawal), and behavioral performance measures alone.

CONFIDENTIAL

This material is the property of the University of Pennsylvania. Do not disclose or use except as authorized in writing by the study sponsor

H2b: The relative contribution of domain-specific brain signal (WM, food cue reactivity and food reinforcement) to the prediction of abstinence challenge-induced increase in caloric intake will be evaluated (regression model).

EXPLORATORY AIM (between group): To provide a baseline comparison in food-related brain response between smokers and non-smokers.

This study will: (a) drive new insights about how the brain can constrain or promote the ability of smokers to prevent PCWG; and (b) lead to new theories and interventions that integrate neural and behavioral frameworks important for promoting behavior change. Support for our predictions would inform testing of novel approaches to prevent PCWG, such as computerized neurocognitive exercise training to increase DLPFC activity and shift activity away from reward sensitive brain networks.

2.2 Overall Objectives - (Recruitment & Retention Pilot Study)

Aim 1: To evaluate the effects of information provision and incentives, alone and in combination, on study enrollment rates.

Hypothesis: Behavioral economic interventions will (Information provision & contingency management) will produce higher rates of enrollment compared to standard recruitment.

3 Study Design

General Design – Main Study

This is a within-subject cross-over neuroimaging investigation of 3 potential neural mechanisms of increased caloric intake during initial smoking cessation. Eighty smokers will be scanned on 2 occasions: (1) after 4 days of monitored abstinence (biochemically verified), and (2) after 4 days of smoking as usual (order counterbalanced) (**Figure 3**). In addition, 30 healthy non-smokers (matched for sex, age, and education) will complete one period of the study to serve as a baseline comparison group (see Exploratory Aim). As in prior studies, participants will have fasted overnight and be provided with a standard meal (BOOST® shake) when they arrive on testing days 4 and 32. Blood oxygen level dependent (BOLD) fMRI sessions will assess BOLD signal at rest and while performing tasks for food cue reactivity, food reinforcement (choice task), and working memory (N-back). Additional measures will be administered out of scanner (**Figure 3**). Caloric intake will be assessed on days 1-3 and 29-31 using a validated dietary recall procedure (days 4 and 32 are fMRI scan days and intake will be standardized). Caloric intake is the primary behavioral outcome. Task-induced BOLD signal change in hypothesized regions of interest and performance on the working memory, food cue, and food reinforcement tasks are the mechanistic variables.

CONFIDENTIAL

This material is the property of the University of Pennsylvania. Do not disclose or use except as authorized in writing by the study sponsor

Figure 3

Non-smoker Control Group (Baseline):

Day	-7	1 2 3 4
Activity	Intake	Period 1*

*non-smokers complete phase 1 with identical monitoring and assessment

**order of periods (abstinence vs smoking) is counter balanced

Smoker Group (within-subject):

Day	-7	1 2 3 4	5-28	29 30 31 32	1 Month Follow-up
Activity	Intake	Period 1	Washout	Period 2	Web-based Survey
State	Smoke	Abstain**	Smoke	Smoke	N/A

Behavioral Outcome:

- Caloric intake (dietary recall; Days 1-3* & Days 29-32)

Intermediate Outcomes: Day 4* & Day 32

- Food reward (out of scanner)
- Working memory (fMRI)
- Food cue reactivity (fMRI)
- Food reinforcement (fMRI)

Smoking Behavior: Days 1-4* and 29-32

- Self-reported (CO-verified)

Recruitment & Retention Pilot

This pilot study will utilize a randomized controlled trial design to evaluate two components of behavioral economic strategies to improve recruitment and retention. To be eligible for the pilot study participants must meet all eligibility criteria for one of the four participating studies (828958, 824061, 824860, 828125), have a phone capable of receiving SMS messages, and consent to receive SMS messages. ~576 participants will be enrolled across the four participating research studies. All subjects will receive standard text messages and will be randomized to one of four groups (blocked within each study to ensure balanced groups): (1) Standard recruitment (SR): subjects will receive text messages ~2 days prior to their Intake visit with relevant information about the time, date, and location of the visit as well as contact information for study staff ("You have a study visit on [Date] at [Time]. Visit comp is \$10. Reply Y to confirm. See <http://j.mp/2222222> for reminders. Reply or appt may be canceled."); (2) SR + Information Provision (IP): Subjects will receive personalized messages designed to target injunctive norms regarding participating in research (e.g., "[Name], wondering why you should volunteer for research? Many find it a rewarding way to advance science and be a part of a community <http://j.mp/2222222>."); (3) SR + Contingency Management (CM): CM will be provided in the form of an opaque "fishbowl" with a high proportion of chips with little (\$1) monetary value. Participants draw from the fishbowl upon completion of an objectively verified target behavior (e.g., attending an Intake visit), and bonuses are often provided for continued performance [74, 75]. This strategy has been successful in augmenting visit compliance in several treatment studies [80-82]. All text reminders will be delivered using the Way 2 Health (W2H) software platform. Upon completion of all requirements for a given visit, participants will receive 5 fishbowl draws for that visit. Attendance at all visits earns participants bonus draws upon completion of the study. Failure to attend a visit without prior approval or failure to complete all visit requirements results in no draws for that visit. The fishbowl contains 500 chips: 250 say "good job," 219 have a value of \$1, 30 have a value of \$5, and 1 has a value of \$100. The study completion bonus will be 5 extra draws. Thus, at each visit, subjects will have the opportunity to make 5 draws from the fishbowl, for maximum possible earnings of \$120; (4) SR + IP + CM (IC): In this group, subjects will receive the targeted text messages and receive CM.

CONFIDENTIAL

This material is the property of the University of Pennsylvania. Do not disclose or use except as authorized in writing by the study sponsor

The design of our study allows us to examine each strategy independently as well as combined to evaluate the optimal approach.

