4.3 Inclusion Criteria

1. Male and female participants who are between 18 and 65 years of age.
 1. Smoking group – 80 smokers who self-report smoking at least 5 cigarettes (menthol and/or non-menthol) per day for at least the last 6 months. Smoking status will be confirmed by CO greater than or equal to 8 parts per million (ppm) at the Intake Visit.
 2. Non-smoking group - 30 individuals reporting fewer than 100 lifetime cigarettes and not even a puff of a cigarette for a minimum of 2 years. Smoking status of non-smokers will be confirmed by CO less than 5ppm. They will be matched to the smoker group on age, sex, and education.
2. Plan to live in the area for the duration of the study (i.e. ~8 weeks/2 months).
3. Capable of giving written informed consent, which includes compliance with the requirements and restrictions listed in the combined consent and HIPAA form.
4. Able to communicate fluently in English (i.e. speaking, writing, and reading).

CONFIDENTIAL

This material is the property of the University of Pennsylvania. Do not disclose or use except as authorized in writing by the study sponsor

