5.1 Telephone Eligibility Screen

Individuals interested in study participation will be screened by a qualified member of the research team to determine initial study eligibility. If the participant meets preliminary eligibility, they will be invited to schedule an Intake Visit at which their final eligibility will be confirmed.

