Weight		x	x	x			x		x			x		
Medical History Form***		x												
fMRI Medical Hx. Form***		x												
Magnet Safety Form***		x					x					x		
Emergency Contact Form***		x												
Demographics***		x												
ETOH History***		x												
Smoking History/Nicotine Dependence (FTND)***		x*												
Smoking Rate (TLFB)			x*	x*	x*	x*	x*		x*	x*	x*	x*		
Cigarette Brand Form***		x*												
Shipley Institute of Living Scale (SILS)***		x												
Carbon Monoxide (CO)		x	x*	x*	x*	x*	x*		x*	x*	x*	x*		
Eating Behavior (DEBQ)***			x				x					x		
Eating Inventory-Disinhibition (EI-D)***				x			x					x		
Depression Symptoms (CES-D)***				x										
Smoking Urges/Craving (QSU-B)***			x	x*	x*	x*	x*		x*	x*	x*	x*		x
Weight Concerns***			x											
Debriefing Phone Call													x	
MECHANISMS														
Working Memory			x				x* *					x**		
Food Reward			x											
Preferred Snack Choice (Pre-RRVF)			x											
Food Reinforcement (RRVF)							x* *					x**		
Pre-FCQ-S			x											

CONFIDENTIAL

This material is the property of the University of Pennsylvania. Do not disclose or use except as authorized in writing by the study sponsor

Food Cue-Induced Craving (FCQ-S)							x*					x**		
Withdrawal Symptoms (MNWS)* ***			x	x	x	x			x	x	x	x		x
Positive and Negative Affect Schedule (PANAS)***			x	x	x	x			x	x	x	x		x
Readiness/Intention to Quit Smoking***														x
Smoking-Related Eating and Episodes test (SWEET)***														x
PRIMARY OUTCOMES														
Caloric Intake (Dietary Recalls)				x	x	x			x	x	x			
% Eligible at Intake (pilot)	x													
SECONDARY OUTCOMES														
Attitudes towards research (pilot)	x													

*Smokers only

**Assessed in fMRI

***Denotes measures that can and will be collected remotely using REDcap.

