Working Memory N-Back Task. Based on our prior work, the primary performance measure will be correct reaction time, and the secondary measure will be number correct; the primary regions of interest for the BOLD analysis will be DLPFC and medial/frontal cingulate gyrus.

Primary Outcomes (Recruitment & Retention Pilot Study):

Meeting Eligibility Criteria: The primary outcome is the percentage of subjects who meet final eligibility criteria (i.e., enrollment). We chose this as the outcome based on our data suggesting that subjects who meet these criteria are highly likely to reach ITT status.

Secondary Subjective Outcomes (Recruitment & Retention Pilot Study):

Impressions of Research: Attitudes towards research; motivations for participation; perceived risks/benefits of research; and perceptions of influence or coercion will be assessed via text survey at baseline (following phone screen), mid-way through participation and at study completion. All secondary outcomes will be delivered via the W2H platform and imported into REDCap. Study staff will attempt to contact subjects who withdraw or are lost-to-follow up to identify reasons for withdrawal. We will assess overall satisfaction with the study, acceptability of the frequency and content of messages (IP and IC groups only). For all models, a term will be included for individual study as well as other relevant covariates (e.g., sex, age, income).

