Aim 3 begins with the model in Aim 2b above, and tests interacting effects of working memory-related BOLD signal and food reinforcement (or food cue reactivity) on food intake. We will reduce the complexity of this analysis by using difference scores (pre minus post) to model a 2-way interaction between working memory and food reinforcement on food intake. We will only test for brain ROIs found to be sensitive to treatment in Aim 1; the number of tests for interaction is uncertain. We anticipate that these effects will be positively correlated and will use the Hochberg step-up procedure, which is robust to correlations among outcomes in the range we expect. For purposes of power calculation, we assumed a correlation of 0.5, which resulted in a corrected p-value of 0.02 for 5 tests. Keeping the independent variables continuous, we can detect an interaction term (one-sample per subject, standardized) of $d=0.36$ with 80% power. Literature estimates for similar interactions were 0.65, 0.66, and 0.35. The lowest estimate gives 77% power, and the average (0.55) yields 98% power.

Recruitment & Retention Pilot Study:

Power is provided for our primary aim. The analysis will compare the enrollment rates between the four intervention arms, and examine main and interaction effects. For SR arm, we expect a 28% of subjects who schedule an intake will be eligible and enroll (based on existing data across the four studies). With the proposed sample of 576, we have $>80\%$ power ($\alpha=.05$) to detect a difference between the SR arm and the IP and CM arms of 12%, corresponding to an OR of 1.75. For the interaction term, we have 80% power ($\alpha=.05$) to detect a departure from additivity of the main effects corresponding to a ratio of odds ratios (ORR) of 5.5.

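### The pilot's entry rule asks for all eligibility criteria to be met already, which contradicts a primary outcome that counts who meets final eligibility

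*Combined protocol and SAP*

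**What the plan says.** **Entry rule** (section 3, Recruitment & Retention Pilot): to be eligible for the pilot, "participants must meet all eligibility criteria for one of the four participating studies". The sentence does not limit this to initial or telephone-screen eligibility.

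**Primary outcome** (section 5.4.3, pilot paragraph): "The primary outcome is the percentage of subjects who meet final eligibility criteria (i.e., enrollment").

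**When final eligibility is settled.** Section 5.1 says of people who pass the telephone screen that "they will be invited to schedule an Intake Visit at which their final eligibility will be confirmed". Some criteria can be met only there. For smokers, section 4.3 states: "Smoking status will be confirmed by CO greater than or equal to 8 parts per million (ppm) at the Intake Visit". Section 4.4 adds a urine drug screen and breath alcohol at the same visit.

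**When the intervention starts.** Section 3 says of standard recruitment (SR), which every arm receives, that "subjects will receive text messages ~2 days prior to their Intake visit". Attending Intake is its example of a behaviour that earns fishbowl draws.

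**Power** (section 5.5), for the SR arm: "we expect a 28% of subjects who schedule an intake will be eligible and enroll". With 576 people the plan claims more than 80% power for a 12-point difference, given as an odds ratio of 1.75.

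**The concern.** The entry rule conditions on the outcome. If everyone admitted already meets every criterion of a parent study, everyone also meets final eligibility, and no arm can differ from another. The rule also cannot be applied when it is needed, because the messages go out before the tests that decide eligibility.

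What is at stake is the denominator of a randomised comparison. Section 5.6 gives no pilot analysis population and no rule for people who miss Intake. The pilot's analysis is described only in section 5.5 (arm comparison, main and interaction effects) and section 5.4.3 (a term for parent study, plus covariates). An analyst who applied the section 3 sentence after the fact would remove people who did not attend or who failed at Intake. That selects on a post-randomisation event which reminders and incentives are meant to change. Four studies share the pilot, so they need one written definition.

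**Working it through.** **Inputs.** SR rate 28% of those who schedule an intake, difference 12 points (so 40%), N = 576, alpha 0.05 (section 5.5); four balanced groups (section 3), so 144 per arm and 288 per level of each factor. Sidedness is not stated for the pilot; two-sided is assumed, as for the main study in section 5.5.

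**1. Reproduce the plan's power.** With n per group and p̄ the mean of the two rates:

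- SE₀ = √[2p̄(1−p̄)/n] = √[2(0.34)(0.66)/288] = 0.0395
- SE₁ = √{[p₁(1−p₁) + p₂(1−p₂)]/n} = √[(0.2016 + 0.2400)/288] = 0.0392
- Power = Φ[(0.12 − 1.96 × 0.0395)/0.0392] = Φ(1.09) = 86%

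An odds ratio of 1.75 from 28% implies 40.5% rather than 40%, and power 89%. If 28% and 40% are instead taken as cell rates with effects additive on the logit scale, the combined arm is 53.3%, the margins are 34% and 46.7%, and power is 87%. The claim of more than 80% holds as a main-effect comparison. A single pair of arms, 144 versus 144, would give 58%, so the figure must be read as a main effect; that does not bear on the present point.

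**2. Apply the entry rule literally.** Then p = 1.00 in every arm, the difference is 0, the variance p(1−p) is 0, and power is undefined. The plan's own inputs imply about 144 × 0.28 = 40 enrolled in SR and 144 × 0.40 = 58 in the information or incentive arm. Neither count is possible under the rule.

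**3. Find the intended population.**

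| Place | What it implies about entry |
|---|---|
| Section 3, text timing | Messages about 2 days before Intake, so entry precedes final eligibility |
| Section 5.4.3, secondary outcomes | Baseline survey follows the telephone screen |
| Section 5.5 | Denominator is people who schedule an intake |
| Section 5.2.8, debriefing call | Pilot enrollees are called after their last session, including after withdrawal or ineligibility |
| Section 3, entry sentence | All criteria already met |

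Four agree with entry at the screening stage. Only the entry sentence does not.

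**4. What dropping people would do.** Write the enrolment rate as a × e, where a is the chance of attending Intake and e the chance of being found eligible on attending. The documents give neither separately. Suppose, as an illustration, that the intervention moves only a. Then 28% = a₀e and 40% = a₁e, so a₁/a₀ = 40/28 = 1.43. Restricted to attenders, both arms show e and the difference is 0. Restricted further to those found eligible, both show 100%.

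**The case against.** The strongest reply is that the literal reading cannot be carried out. The protocol separates initial eligibility by telephone from final eligibility at Intake; the outcome says final and the entry sentence does not. With the text timing, the survey after the screen, the 28% of those who schedule, and the debriefing of people later found ineligible, a careful reader reaches the right population. No passage proposes dropping randomised people, and a 28% rate makes sense only if failures stay in the denominator. All of this stands as evidence of intent. It does not make the entry sentence correct, because that sentence asks for all criteria and several are tested only at Intake.

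Three stronger readings are not supported:

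- A reader might infer that the pilot will produce 100% in every arm and has no power. That is the consequence of the words, not the likely conduct.
- A reader might infer that three places define three rival populations, because Table 2 marks the outcome "Eligible at Intake (pilot") only under Phone Screen. Table 2 defines no population. Its pilot rows are also a poor guide to timing: attitudes to research carry the same single mark, although section 5.4.3 collects them at three times.
- A reader might set 148/375 = 39% from section 4.2 against the 28%. That ratio counts people who consent in this one study. Section 5.2.2 takes consent at Intake, so non-attendance is left out (section 10.3 moves consent ahead of the visit only for later enrolment). No pilot passage uses consenters as its denominator.

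**Conclusion.** The entry rule is wrong as written. It contradicts the primary outcome, cannot be satisfied before the intervention begins, and is incompatible with the 28% control rate. The rest of the protocol shows that people who pass the telephone screen and schedule an Intake Visit were meant, so this is a wording error with a clear repair. The risk is to validity if the sentence is applied literally at analysis; the size of the pilot is unaffected, with main-effect power about 86% at 28% versus 40% and 288 per level.

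This rests on two assumptions. The exact 100% requires that all eligibility criteria include the Intake tests, as they do in this protocol; the criteria of the other three studies are not in the documents. On a looser reading of the sentence, non-attendance would keep the rate below 100%. The power figure assumes a two-sided main-effect comparison.

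**What to change.** 1. In section 3, restate pilot entry as initial (telephone-screen) eligibility for one of the four participating studies, with an Intake Visit scheduled.
2. In section 5.4.3, define the primary proportion as the number finally eligible divided by all randomised in the arm, with people who do not attend Intake or who fail there counted as not enrolled, and no one removed after randomisation.

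The cost is two sentences. No new data are needed, and N = 576 and the power inputs in section 5.5 stay as they are, since that section already uses people who schedule an intake.
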